#### **8.4.1 Degree of Exposure**

Degree of Exposure will be based on all patients that accomplished selection criteria and receive at least one drug dose (full analysis set)

EudraCT number: 2016-001888-36

- b: "Actual Cycle Duration" is the treatment duration for a cycle per CRF. It is the length of time (days) between actual and next cycle start date dose. At the last cycle is the difference between start and stop date dose.
- c: "Actual Total Dose per Cycle" is the total dose a patient actually took in a cycle (55 kBq/kg). No adjustment of dose level is permitted.
- d: "Intended Cycle Duration" is equal to 28 (+/- 7 days), except for the last cycle that is the minimum of 28 (+/- 7 working days) and Actual Cycle Duration
- f: "Intended Cycle Dose Days" is equal to 1, except for the last cycle that is the minimum of 1 and Actual Cycle Duration.
- A: "Total number of cycles". 6 cycles are expected for each patient.
- B: "Treatment Duration" = Sum over all cycles of (b).
- C: "Total Actual Dose" = Sum over all cycles of (c).
- D: "Total Intended Duration" = Sum over all cycles of (d).
- F: "Total Intended Dose Days" = Sum over all cycles of (f).
- K: "Ratio For Cycle Duration" = D/B

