6. STUDY DRUG INFORMATION

6.1. Study treatment

Once enrolled in the study, the patient will receive study treatment.

Patients will be treated with radium-223 at a dose of 55 kBq (1.49 microcurie) per kilogram body weight, given at four-week intervals for six IV injections.

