6.8. Dose administration

Before administration of study drug, the patient must be well hydrated and should be instructed to drink ad libitum. Aseptic technique should be used in the administration of radium-223. The syringe should be handed over to the individual who will perform the injection. The study medication will be administered as a slow bolus IV injection over one minute. After administration, the equipment used in connection with the preparation and administration of drug is to be treated as radioactive waste and should be disposed in accordance with hospital procedure for the handling of radioactive material. Information about radium-223 and instruction about handling and injection of radioactive material will be given to study personnel.

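### SAP 8.4.1 makes Total Intended Dose Days one too few for every patient and leaves the cycle-duration ratio undefined after a single injection

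*SAP*

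**What the plan says.** SAP 8.4.1 builds the exposure summary from per-cycle quantities.

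- **Actual duration, b.** For cycles before the last: "It is the length of time (days) between actual and next cycle start date dose". For the last cycle: "At the last cycle is the difference between start and stop date dose".
- **Intended duration, d.** 28 days with a window, "except for the last cycle that is the minimum of 28 (+/- 7 working days) and Actual Cycle Duration".
- **Intended dose days, f.** This "is equal to 1, except for the last cycle that is the minimum of 1 and Actual Cycle Duration".
- **Totals.** B, D and F are the sums of b, d and f over cycles, and K = D/B. A is the number of cycles, with the remark that "6 cycles are expected for each patient". C is the total dose actually given.

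The section covers every eligible patient who has had one dose or more. It gives no inclusive (+1 day) counting rule and does not say what to do when B = 0.

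Protocol 6.8 describes each administration: "The study medication will be administered as a slow bolus IV injection over one minute". Protocol 6.1 sets the regimen: "given at four-week intervals for six IV injections".

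**The concern.** A min(1, duration) cap makes sense for a drug taken over several days, where the duration of the last cycle counts days of dosing. For a single injection that starts and stops on the same date, the duration is 0 and the cap removes the dose day. The section then disagrees with itself: a fully compliant patient has six cycles, each meant to carry one dose day, but five intended dose days in total.

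A patient who stops after one injection has zero in both the numerator and the denominator of K. The Protocol allows early discontinuation (3.2, 5.5, 6.11), so such patients are foreseeable.

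Exposure is the first level of the safety analysis (Protocol 8.5, SAP 8.4.3), where it is used to judge how far safety can be assessed at all. SAP 8.1 also promises independent checking of outputs. Without a stated convention, one programmer could subtract dates and another count inclusively, and the two would get different tables from the same data.

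**Working it through.** The documents state no value for B, D, F or K. The nearest stated figure is A = 6 cycles with one dose day each, which implies six intended dose days.

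**Inputs**

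- Planned injections: 6, at intervals of 4 weeks = 28 days (Protocol 6.1).
- Length of one administration: one minute, so dose start date = dose stop date (Protocol 6.8).
- b for cycles before the last: the interval to the next injection (SAP 8.4.1).
- b for the last cycle: stop date minus start date = 0 by plain subtraction (SAP 8.4.1).
- d before the last cycle: taken as 28. The window on d is given both as 7 days and as 7 working days in the same item; this does not affect the last cycle.

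**Last cycle**

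- b = 0
- d = min(28, 0) = 0
- f = min(1, 0) = 0

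**Totals for n injections given exactly on schedule**

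- B = 28 × (n − 1)
- D = 28 × (n − 1)
- F = n − 1
- K = D/B

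| Injections n | B (days) | D (days) | F as written | One dose day per injection | K |
|---|---|---|---|---|---|
| 1 | 0 | 0 | 0 | 1 | 0/0, undefined |
| 2 | 28 | 28 | 1 | 2 | 1.00 |
| 3 | 56 | 56 | 2 | 3 | 1.00 |
| 6 | 140 | 140 | 5 | 6 | 1.00 |

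The shortfall in F is always one day. In relative terms it is 1/6 = 17% after six injections, 1/3 = 33% after three and 1/1 = 100% after one.

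**Delayed dosing.** Six injections at 35-day intervals give B = 5 × 35 = 175, D = 5 × 28 = 140, F = 5 and K = 140/175 = 0.80. K still measures delay correctly here, because the last cycle adds zero to both sums.

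**Sensitivity to the counting convention (an assumption the SAP does not make).** If the last cycle were counted inclusively, as stop − start + 1 = 1 day, six injections would give B = 141, D = 141, F = 6, K = 1.00. One injection would give B = 1, D = 1, F = 1, K = 1.00. Both faults would disappear, so they depend on plain subtraction, which is the ordinary reading of a difference between two dates.

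**The case against.** Most of the exposure summary is sound, and the objections to any wider criticism largely stand.

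- **Zero time after the last injection is not an error.** Protocol 3.5 defines the treatment period as running from first dose to last dose. Six on-time injections give 140 days = 20 weeks, the same figure that Protocol 1.2 reports for six cycles in the pivotal radium-223 trial.
- **No administered injection is lost.** F is an intended quantity. A and C count every injection, including the last, and no other listed quantity uses F; in particular K does not.
- **The undefined ratio is narrow and visible.** K fails only for patients with exactly one injection. SAP 7.3 reports a count of unavailable values for exposure, and SAP 8.3 lists all dropouts with their drug exposure. A ratio of intervals also has no meaning for someone with no interval.
- **The eCRF is not in the documents.** How the dose stop date is recorded, and whether the programmed difference is inclusive, cannot be checked.

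A reader might go further and infer that exposure is understated for every patient, or that early stoppers drop out and bias the summary toward completers. The documents do not support either reading. The universal understatement applies to F alone. A one-injection patient still contributes one cycle and a full injected dose. The only omission is from the mean and median of K, and it is shown by the count of unavailable values.

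What the objections do not remove is that the written rule for F gives a number that contradicts the section's own allowance of one dose day per cycle, and that no convention is given for B = 0.

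**Conclusion.** The rule is wrong as written, with a small and well-bounded effect. F is n − 1 rather than n for every patient (5 instead of 6 for a completer, 0 instead of 1 after a single injection), and K is undefined for one-injection patients. How many such patients there will be cannot be known from the documents.

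The conclusion assumes that the recorded stop date of an injection is the injection date and that the difference is plain subtraction. The first follows from the one-minute bolus. The second is the natural reading but is not confirmed.

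B, A, C, and K for two or more injections stand as they are. Both affected items are descriptive; no efficacy result, adverse event table or analysis denominator changes. This is a tidy-up worth making, of low priority.

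**What to change.** Amend SAP 8.4.1 in two places.

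1. Set intended dose days to 1 for every cycle, including the last, so that F equals the number of injections. A completer then has F = 6 and a one-injection patient F = 1.
2. Define K over the intervals between consecutive injections only: planned days divided by actual days, summed over cycles 1 to n − 1. Report patients with one injection as not applicable and give their number. For two or more injections K is unchanged (1.00 on schedule, 0.80 at 35-day intervals).

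Leave B as the time from first to last dose. Crediting the last cycle with 28 days in both B and D would also make K computable, but it should be avoided. It departs from Protocol 3.5 and dilutes delays: six injections at 35-day intervals would give (140 + 28)/(175 + 28) = 168/203 = 0.83 instead of 0.80.

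The cost is a sentence or two of SAP wording and a few program lines. No new data, protocol amendment or change to patient management is needed.

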#### **8.4.2 *Concomitant Medications***

The number and percent of unique patients taking concomitant medications will be summarized by ATC code. Elective surgeries/procedures performed during the study will be presented in a listing.

The following are conventions that will be used to classify individual medications as prior and/or concomitant:

- Medications with stop dates prior to enrollment will be considered prior.
- Medications with missing stop dates or stop dates the day of or after enrollment will be considered concomitant, regardless of start date. Additionally, if the start date is prior to enrollment or missing, the medication will also be considered prior.

Frequencies and by-subject listing of all prior and concomitant medications will be provided, containing variables listed on Prior/Concomitant Assessment eCRF, their corresponding categories (Prior or Concomitant), and WHO Anatomical Therapeutic Chemical (ATC) level 4.

#### **8.4.3 *Adverse Events***

All AEs will be recorded on the eCRF "Adverse Events" page and will be coded using the current version of MedDRA® to give a system organ class (SOC) and preferred term (PT) for each event. All adverse event safety data will be updated to the version of MedDRA that is current at the time of the database lock and statistical analyses. Adverse events will be coded with grades defined according to CTCAE V4.0 criteria.

Treatment-emergent AEs (i.e. those events occurred after the first study medication administration and were not present at baseline or worsened in severity following the start of treatment) will be tabulated. The TEAE will be tabulated according to intensity and causality. If intensity of an AE or causality of an AE to the study medication is missing, a worst-case scenario will prevail (severe in intensity or probably related will be assumed). In the summary tables the number of subjects with events and the number of events will be presented.

The onset date of an AE will be compared to the date of first dose of study drug to determine whether or not the AE is treatment-emergent. Adverse events with an onset date on or after the date of first dose of study drug will be classified as treatment-emergent.

All deaths and SAEs, regardless of cause, from treatment up to three months after study discontinuation will be assessed. Non-fatal AEs occurring after treatment start regardless of cause, up to three months after study discontinuation or until start of new anti-cancer treatment, whichever is first will be assessed. SAEs and hospitalizations related solely and unequivocally to the progression of the established tumor disease will not be treated as SAEs as per protocol. Events that are continuations of baseline abnormalities are considered treatment emergent adverse events only if there is an increase in grade over baseline, or if there is an increase following a decrease during the study.

Treatment emergent adverse events with cause possibly related to treatment as judged by the investigator will be considered related to treatment. Events that are continuation of baseline abnormalities will not be considered treatment related unless there is an increase in grade, or if there is an increase following a decrease, and the increase is judged by the investigator to be due to treatment.

The following summaries will be provided:

- An overview of adverse events (number of subjects with at least one AEs, number of subjects with at least one TEAE, number of subjects with serious TEAE, number of subjects with non-serious TEAE, number of deaths, number of subjects with TEAE leading to discontinuation of study treatment, number of subjects dropped out due to AE).
- A summary of the number and percentage of subjects reporting a treatment-emergent adverse event by treatment group, SOC, and PT.

- A summary of the number and percentage of subjects reporting a treatment-emergent adverse event related to study drug by treatment group, SOC, and PT.
- A summary of the number and percentage of subjects reporting a treatment-emergent adverse event by treatment group, by maximum intensity, SOC and PT.
- A summary of the number and percentage of subjects reporting a serious treatment-emergent adverse event, by treatment group, SOC and PT.
- A summary of the number and percentage of subjects reporting a treatment-emergent adverse event resulting in death during the study, by treatment group, SOC and PT.
- A summary of the number and percentage of subjects with adverse events leading to discontinuation of study drug, by treatment group, SOC and PT.  
For adverse events, we will report intensity, relationship to study drug, body system, action taken, and outcome.  
Serious adverse events, deaths and study discontinuations will be described and examined for full analysis set.

Analysis of safety-related data will be considered at four levels:

- First, the extent of exposure (dose, duration, number of patients) will be examined to determine the degree to which safety can be assessed from the study.
- Second, we will describe and compare clinically relevant test, concomitant medications and adverse events reported in the full analysis set. For adverse events, we will report intensity, causality, relationship to study drug, body system, action taken, and outcome.
- Third, serious adverse events, deaths and study discontinuations will be described and examined in the full analysis set.
- Fourth, the occurrence and maximal grade of toxicity for the whole duration of treatment will be listed and tabulated by type. Adverse events reported as non-drug related by the responsible investigator will be reported as well.

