Definition of hospitalization: AEs that require hospitalization are considered serious. In general, hospitalization is considered as such when the patient has stayed (usually overnight) at a hospital or emergency room for observation or treatment that could not have been performed in a doctor's office or outpatient site. If there is some doubt as to whether the hospital stay can be considered "hospitalization" or whether it was necessary or not, the AE should be considered serious.

Hospitalization for scheduled surgery or standard clinical procedures which are not the result of an AE will not be considered an AE. If an incident arises during the procedure that is considered harmful, this should be reported as an AE and should be designated "serious" or "not serious" as per the standard criteria.

Definition of an event that is clinically or medically significant: Significant medical events that do not have a fatal outcome, regardless of whether they are life-threatening or require hospitalization, may be considered SAEs when, according to the appropriate medical opinion they put the patient's life at risk and may require medical or surgical intervention to prevent any of the outcomes listed in this definition. Examples of such medical events include allergic bronchospasm which requires intensive treatment in an emergency room or at home; blood dyscrasias; convulsions that do not result in hospitalization; or development of drug dependency or drug abuse. Clinically/medically significant events must be reported as SAEs.

For this clinical study and, according to this protocol, SAEs and hospitalizations related solely and unequivocally to the progression of the established tumor disease will not be treated as SAEs with regards to reporting obligations.

If the investigator becomes aware of a SAE at any time after the end of administration of study treatment and believes that it is possibly related to the study treatment (serious adverse reactions), he/she should notify the Sponsor.

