7.2. Reporting of AEs

AEs will be collected starting from the first procedure required by the study up to three months after patient's disease progression. Safety evaluation after progression will include follow-up of symptomatic skeletal related events until reach 2 years from the last dose of study treatment.

All study patients who experience AEs will be closely monitored during this time. All AEs should be recorded in the CRF.

All signs, symptoms, and results of procedures with abnormal diagnoses that are clearly related should be grouped together and reported as a single diagnosis or disorder wherever possible. Any other event that does not fulfill this definition will also be reported separately.

Reporting of SAEs and reporting period

Reporting requirements will comply with all applicable local regulations regarding safety reporting.

All SAEs and AESIs defined in the protocol will be reported to the Sponsor within a period of 24 hours from the time the investigator or any other member of the site staff becomes aware of the event, as follows:

- Regardless of the study drug received by the patient and whether or not the investigator considers this event to be related or not to the study drug, all SAEs and AESIs (as defined in this protocol), will be reported to MedSIR immediately, no later than 24 hours after any member of the study site staff becomes aware of the event.
- All information regarding the SAE and AESI should be obtained and recorded in full using the SAE form and sent to MedSIR.
- Follow-up information, copies of test results, event outcome and the opinion of the investigator as to the relationship between the IMP and the SAE and AESI, accompanied by other applicable documentation when it is requested, will be sent along with the SAE form, if available on the day the event is reported or as soon as possible if it is not.
- The original SAE reporting form of the Sponsor should be kept on file with the documentation from the CRF at the study site(s).

All SAE forms will be sent by the investigator or investigator staff to the Sponsor by e-mail and fax as indicated below:

E-mail: [contact]

Fax: [name]

Follow-up of the SAEs and AESIs will continue until they resolve, a stable outcome is reached, patient is lost to follow-up, or the patient dies.

MedSIR will be responsible for ensuring that events are reported to the European Medicine Agency (EMA), competent authorities, within the stipulated period, as needed.

AESIs

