8.5. Safety results

All safety data will be evaluated at the first 34 months period of the study. Additionally, symptomatic skeletal related events will be evaluated at the 2-years safety extension after the end of the treatment.

Analysis of safety-related data will be considered at three levels:

- First, the degree of exposure (dose, duration, number of patients) will be assessed to determine the degree to which study safety can be assessed.
- Second, clinically relevant tests, concomitant medications, and reported AEs will be described. For AEs, severity, expectedness, causality, relationship, body system, action taken, and outcome will be reported.
- Third, SAEs, deaths, and study discontinuations for each study group will be described and assessed.

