#### 7.1.1 *Primary analysis*

The primary efficacy endpoint is the median PFS achieved with radium-223 treatment. The PFS will be evaluated at the first 34 months period of the study. The PFS will not be evaluated at the 2-years extension of the study for safety.

PFS is a composite endpoint defined as the time from the start of the radium-223 treatment to disease progression in bone or soft-tissue, symptoms, or death, according to the modified PCWG2 criteria.

Objective radiographic disease progression is defined as the presence of at least one of the following conditions:

- Bone lesion progression (appearance of  $\geq$  two new bone lesions compared to baseline).
- Soft-tissue lesion progression according to the RECIST criteria version 1.1.
- Presence of symptomatic skeletal events (pathological fractures, spinal cord compression, radiation or surgery to bone), which should have been reported as adverse event/serious adverse events.

Patients with no progression will be censored at the date of their last evaluation (see Table 1 – Appendix I).

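### SAP 8.4.3 turns a reporting-only exemption into an analysis rule, so skeletal events can be under-counted as serious, and the SAP names no symptomatic-skeletal-event analysis for the extension

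*SAP*

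**What the plan says.** SAP 8.4.3 holds three rules in one paragraph:

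- On deaths and serious events: "All deaths and SAEs, regardless of cause, from treatment up to three months after study discontinuation will be assessed".
- On non-fatal AEs, the window closes "up to three months after study discontinuation or until start of new anti-cancer treatment, whichever is first".
- On progression: "SAEs and hospitalizations related solely and unequivocally to the progression of the established tumor disease will not be treated as SAEs as per protocol".

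The protocol source of the third rule is Protocol 7.1, under which such events "will not be treated as SAEs with regards to reporting obligations".

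SAP 7.1.1 lists symptomatic skeletal events (pathological fracture, cord compression, radiation or surgery to bone) among the conditions that count as progression for PFS, and adds of them: "which should have been reported as adverse event/serious adverse events".

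On collection, Protocol 7.2 says "AEs will be collected starting from the first procedure required by the study up to three months after patient's disease progression", and it follows skeletal events to 2 years from the last dose. Protocol 8.5 says "symptomatic skeletal related events will be evaluated at the 2-years safety extension after the end of the treatment". SAP 7.3 names bone lesions, not symptomatic skeletal events, as what is evaluated in the extension. SAP 7.2 keeps only OS among the efficacy endpoints there, so time to first SSE stops before it.

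**The concern.** Protocol 3.7 gives the evaluation of skeletal events as the reason for the 2-year extension. They are also the events most likely to be attributed to the tumour, because the SAP itself counts them as progression events. Attribution is made at the sites, without central review (SAP 7.1), in a single-arm trial with no comparator against which to judge it.

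If the SAP removes serious status from progression-related events at the analysis stage, the serious-event table depends partly on each investigator's view of cause. An event that has lost serious status also becomes subject to the earlier cut-off for non-fatal AEs. Time to first SSE does not recover it: that endpoint counts first events only and is not evaluated in the extension.

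**Working it through.** The plan gives no figure to reproduce on this point. The main check is to set the texts against each other.

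**Step 1: scope of the exemption.** Protocol 7.1 switches off a reporting duty. SAP 8.4.3 cites the protocol but omits the words that limit the exemption to reporting, and it places the sentence in the section that defines the AE tables. Protocol 8.5 plans to describe SAEs and contains no such exclusion.

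**Step 2: consistency inside SAP 8.4.3.** One sentence assesses SAEs whatever their cause; a later one withdraws SAE status because of cause. A programmer cannot apply both.

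**Step 3: trace a skeletal event through the rules.**

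| Case | Serious-TEAE table | General TEAE tables |
|---|---|---|
| Before new therapy, keeps SAE status | counted | counted |
| Before new therapy, attributed entirely to progression | lost | counted |
| After new therapy, keeps SAE status | covered by the SAE sentence, which has no new-therapy cut | unclear: the non-fatal AE sentence could be read to cut it |
| After new therapy, non-fatal, and non-serious or stripped of SAE status | not counted | lost |
| Followed only in the 2-year extension | no SSE table named | no SSE table named |

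**Step 4: reach of the new-therapy cut within the AE collection window.** That window runs to 3 months after progression (Protocol 7.2). The inputs are assumptions, except that 6.3 months is the plan's own target median PFS:

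- Exponential time to progression, median 6.3 months: rate ln 2/6.3 = 0.1100 per month, mean 9.09 months.
- Exponential post-progression survival, median m = 8.6 or 14 months: rate λ = ln 2/m = 0.0806 or 0.0495.
- New therapy starts d = 1 or 2 months after progression in a share q = 50% to 100% of patients.

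Patient-time in the 3 months after progression = (1 − e^(−3λ))/λ = 2.67 months (m = 8.6) or 2.79 months (m = 14).

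Patient-time removed = q × (e^(−dλ) − e^(−3λ))/λ.

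- Smallest (m = 8.6, d = 2, q = 0.5): 0.5 × (0.8511 − 0.7852)/0.0806 = 0.41 months; 0.41/(9.09 + 2.67) = about 3.5%.
- Largest (m = 14, d = 1, q = 1): (0.9517 − 0.8620)/0.0495 = 1.81 months; 1.81/(9.09 + 2.79) = about 15%.

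Truncating everything at the end of skeletal follow-up (sixth injection at week 20, or 4.6 months, plus 24 = 28.6 months) gives 3.4% and 15.1%. The range is therefore about 3–15%.

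**The case against.** Much of the opposing case stands.

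- The exemption sentence removes serious status; it does not delete the AE. The SAP tabulates all TEAEs by SOC and PT and by maximum intensity, and also reports events judged unrelated to the drug. A reader might infer that skeletal events fall out of the safety tables altogether. The documents do not support that as a general statement.
- Being a PFS event does not trigger the exemption. It needs a judgement that the event is due to progression alone and beyond doubt, and no passage equates the two. The instruction in SAP 7.1.1 to report skeletal events as AEs or SAEs can even be read as keeping them in.
- The reference to the protocol in the exemption sentence may be meant to carry over the reporting limit. That is a charitable reading, but the sentence as written still conflicts with its neighbour.
- The new-therapy cut sits in the sentence on non-fatal AEs. Events that keep SAE status have their own window without it. Ending other AEs at new therapy is a defensible way to limit confounding by later treatment.
- SAP 7.3 does evaluate bone lesions in the extension, and Protocol 8.2 uses the same term for the same extension. The SAP therefore does not remove skeletal events from the extension; its wording is loose and it names no table for them.

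Two larger figures are tempting. With the whole 28.6-month window as denominator, 21–54% of patient-time falls after new therapy under the same assumptions. However, 37–45% of that window lies more than 3 months after progression, when general AE collection has ended and skeletal events are followed under a separate provision, so that time is not lost through the cut. Assuming that 20–40% of 52 patients have a skeletal event and half of these are hospitalised gives 52 × 0.20 × 0.5 = 5.2 to 52 × 0.40 × 0.5 = 10.4 serious events. Both rates are assumed, and the result is an upper bound because it requires every case to be attributed entirely to progression.

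**Conclusion.** The point holds in limited form. SAP 8.4.3 misstates the scope of the protocol's exemption and contradicts itself on which SAEs are assessed. Followed as written, it can under-count skeletal events in the serious-TEAE table, and it drops from all AE tables those non-fatal events that lack or lose serious status and occur after new therapy. Separately, the SAP names no analysis of symptomatic skeletal events in the extension, although Protocol 8.5 calls for one.

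The number of events affected cannot be given, because the documents contain no skeletal-event rate. The 3–15% is a share of patient-time, not of events. It rests on assumed exponential times and on assumed uptake and timing of new therapy. The correction should be made; it does not affect the primary analysis.

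**What to change.** 1. In SAP 8.4.3, restrict the progression exemption to expedited reporting, as Protocol 7.1 does. Tabulate every recorded event that meets a seriousness criterion, with those judged progression-related shown in a separate row.
2. Add one safety-set table of recorded symptomatic skeletal events regardless of attribution, counted to 2 years after last dose and shown before and after the start of new anti-cancer treatment. In SAP 7.3, replace bone lesions with the term that Protocol 8.5 uses, symptomatic skeletal related events.

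The new-therapy cut for other non-fatal AEs may stay.

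The cost is a few sentences and one table. The protocol already provides for collecting AEs, skeletal events and post-study therapy. The CRF is not among the documents, and exempt events may not have been flagged as serious, so the tables should be described as covering recorded events. The downside is a slightly less favourable SAE table that includes some disease-related events, which the separate row identifies. No treatment or patient-management rule changes.
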